### 7.7. Analysis of Additional Efficacy Parameters

The following additional efficacy endpoints will be summarized descriptively based on the ITT population in the PC period, the open-label evaluable population in the OLE period, and the long-term evaluable population in the LTE period:

- Proportion of participants in each category of Hurley Stage at each scheduled visit
- Proportion of participants with Hurley Stage change from baseline at each scheduled visit
- Mean percent change from baseline in AN count at each scheduled visit
- Proportion of participants achieving HiSCR90 at each scheduled visit

## 9. SAFETY AND TOLERABILITY

Appendix A provides a list of data displays. Sample data displays are included in a separate document.

## 9.1. General Considerations

The analyses in this section will be provided for the safety population in the PC period, the open-label evaluable population in the OLE period, and the long-term evaluable population in the LTE period, unless otherwise specified. Summary tables may be replaced with listings when appropriate. For instance, an AE frequency table may be replaced with a listing if it only contains a few unique preferred terms reported on relatively few participants.

### 9.2. Adverse Events

#### 9.2.1. Adverse Event Definitions

A TEAE is any AE either reported for the first time or worsening of a pre-existing event after the first dose of study drug until the end of the safety follow-up.

TEAE in each period is any AE with a start time after the first dose of study drug in each period and until the end of the safety follow-up, or prior to the first dose in the subsequent period for participants who entered in to the subsequent period. Analysis of AEs (as discussed below) will be limited to TEAEs, but data listings will include all AEs regardless of their timing in relation to study drug administration. For purposes of analysis, all AEs will be considered TEAEs unless the AE can unequivocally be defined as not treatment-emergent.

Adverse events will be tabulated by MedDRA PT and SOC. Severity of AEs will be graded using the NCI CTCAE v5.0. The CTCAE reporting guidelines and grading details are available on the Cancer Therapy Evaluation Program website.

The subset of AEs considered by the investigator to be related to study drug will be considered to be treatment-related AEs. If the investigator does not specify the relationship of the AE to study drug, the AE will be considered to be treatment-related. The incidence of AEs and treatment-related AEs will be tabulated. In addition, serious TEAEs will also be tabulated.

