9.3. Recording and Follow-Up of Adverse Events and/or Serious Adverse Events

Adverse Event and Serious Adverse Event Recording

- An AE/SAE that begins or worsens after informed consent is signed should be recorded on the Adverse Event Form in the eCRF. Conditions that were present at the time informed consent was given should be recorded on the Medical History Form in the eCRF.
- When an AE/SAE occurs, it is the responsibility of the investigator to review all documentation (eg, hospital progress notes, laboratory reports, and diagnostics reports) related to the event.
- The investigator (or delegate) will then record all relevant AE/SAE information in the eCRF.
- It is **not** acceptable for the investigator to send photocopies of the participant's medical records in lieu of completing the AE eCRF page.
- There may be instances when copies of medical records for certain cases are requested. In this case, all participant identifiers, with the exception of the participant number, will be redacted on the copies of the medical records before submission.
- The investigator will attempt to establish a diagnosis of the event based on signs, symptoms, and/or other clinical information. Whenever possible, the diagnosis (not the individual signs/symptoms) will be documented as the AE/SAE. When a clear diagnosis cannot be identified, each sign or symptom should be reported as a separate AE/SAE.

To the extent possible, each AE/SAE should be evaluated to determine:

- The severity grade (CTCAE v5 Grade 1 to 5). See below for further instructions on the assessment of intensity.
- Whether there is at least a reasonable possibility that the AE is related to the study treatment (including study drug): suspected (yes) or not suspected (no). See below for further instructions on the assessment of causality.
- The start and end dates, unless unresolved at final follow-up.
- The action taken with regard to study drug as a result of the AE/SAE(s).
- The event outcome (eg, not recovered/not resolved, recovered/resolved, recovering/resolving, recovered/resolved with sequelae, fatal, unknown).
- The seriousness, as per the SAE definition provided in Section 9.2.
- The action taken with regard to the event. Note: If an AE is treated with a concomitant medication or nondrug therapy, this action should be recorded on Adverse Event Form and the treatment should be specified on the appropriate eCRF (eg, Prior/Concomitant Medications, Procedures and Non-Drug Therapy).

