Follow-Up of Adverse Events and Serious Adverse Events

- The investigator is obligated to perform or arrange for the conduct of supplemental measurements and/or evaluations as medically indicated or as requested by the sponsor to elucidate the nature and/or causality of the AE or SAE as fully as possible. This may include additional laboratory tests or investigations, histopathological examinations, or consultation with other health care professionals.
- If a participant dies during participation in the study or during a recognized follow-up period, the investigator will provide the sponsor with a copy of any postmortem findings including histopathology.
- New or updated information will be recorded in the originally completed eCRF.
- Any updated SAE data will be submitted to the sponsor (or designee) within 24 hours of receipt of the information.
- Once an AE is detected, it should be followed until it has resolved or until it is judged to be permanent; assessment should be made at each visit (or more frequently if necessary) of any changes in severity, the suspected relationship to the study drug, the interventions required to treat the event, and the outcome.
- When the severity of an AE changes over time for a reporting period (eg, between visits), each change in severity will be reported as a separate AE until the event resolves.

See Appendix C for the management of potential Hy's Law cases.

9.4. **Reporting of Serious Adverse Events**

Regardless of suspected causality (eg, relationship to study drug or study procedures), all SAEs occurring after the participant has signed the ICF through the last study visit (or up until the end of the safety follow-up period, whichever occurs later) must be reported to the sponsor (or designee) immediately, without undue delay and not later than within **24 hours** of learning of its occurrence, unless otherwise specified by the Protocol. The investigator will submit any updated SAE data to the sponsor (or designee) immediately, without undue delay, without undue delay and not later than within 24 hours of it being available.

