10.4.3. Safety Analyses

Safety analyses will be conducted for the safety population. A TEAE is any AE either reported for the first time or worsening of a pre-existing event after first dose of study drug until the end of the safety follow-up period. Analysis of AEs will be limited to TEAEs, but data listings will include all AEs regardless of their timing to study drug administration. Adverse events will be tabulated by the MedDRA preferred term and system organ class. Severity of AEs will be based on the NCI CTCAE v5.0 using Grades 1 through 5.

The subset of AEs considered by the investigator to have a relationship to study drug will be considered to be treatment-related AEs. If the investigator does not specify the relationship of the AE to study drug, then the AE will be considered treatment-related. The incidence of AEs and treatment-related AEs will be tabulated.

The clinical laboratory data will be analyzed using summary statistics; no formal treatment group comparisons are planned. Laboratory test values outside the normal range will be assessed for

Version 2

severity based on the normal ranges for the clinical reference laboratory. The incidence of abnormal laboratory values and shift tables relative to baseline will be tabulated. Descriptive statistics and mean change from baseline will be determined for vital signs (ie, blood pressure, pulse, respiratory rate, and body temperature) at each assessment time. Descriptive statistics and mean change from baseline will be determined for each ECG parameters at each assessment time.

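### The period TEAE rule in SAP 9.2.1 goes by start time alone, so an event carried over from an earlier period can be counted as treatment-emergent in the new period merely because its grade fell

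*SAP*

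**What the plan says.** SAP 9.2.1 (Adverse Event Definitions) contains three rules that matter here.

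- General definition: "A TEAE is any AE either reported for the first time or worsening of a pre-existing event after the first dose of study drug". Protocol 10.4.3 has the same wording, "A TEAE is any AE either reported for the first time or worsening of a pre-existing event after first dose of study drug", and no period-specific rule.
- Period definition: "TEAE in each period is any AE with a start time after the first dose of study drug in each period". The window closes at the end of safety follow-up, "or prior to the first dose in the subsequent period for participants who entered in to the subsequent period".
- Default: "all AEs will be considered TEAEs unless the AE can unequivocally be defined as not treatment-emergent".

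Protocol 9.3 governs what becomes a record. When severity changes over a reporting period, "each change in severity will be reported as a separate AE until the event resolves". The items to be determined for each AE include "The start and end dates, unless unresolved at final follow-up". The follow-up list that holds the severity rule also says "New or updated information will be recorded in the originally completed eCRF". Protocol 8.3.1 starts AE recording at informed consent, so records can predate Day 1.

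Under SAP 5.2, OLE tables are grouped by placebo-controlled (PC) treatment, with everyone in the OLE on 75 mg. LTE tables use two groups by initial LTE dose, ≤ 45 mg and ≥ 60 mg. SAP 9.2.2 tabulates participants with TEAEs by treatment group for each period.

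**The concern.** A period TEAE table should show what arose or got worse on that period's treatment. The period sentence tests only when a record starts, and the protocol opens a record at every change of grade, including a fall. Together they make improvement generate a TEAE where persistence does not.

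The OLE and LTE tables are where the long-term safety of the drug will be read. An event that began on placebo, 15 mg or 45 mg and was resolving at the switch could appear there as an event on 75 mg. The PC table is exposed as well: an event that began after consent but before Day 1, and eased after the first dose, meets the period rule although it is neither new nor worse.

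Other safety data are handled differently. SAP 4.1.3 resets the OLE safety baseline for switchers to the last value before the first 75 mg dose. Nothing in the visible text makes the corresponding comparison for AE grade.

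**Working it through.** The plan states no figure on this point, so there is none to reproduce. The check applies the written rules to constructed event histories and then sets a scale.

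**Inputs**

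- One record per grade change: Protocol 9.3.
- Period assigned by record start: SAP 9.2.1.
- Record start taken as the date of the grade change: assumed.
- First OLE dose on Day 113: assumed, from 16 × 7 + 1.
- Group size of about 50: SAP 3.1. The number entering the OLE is not given.

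**Step 1: event histories.** Each event begins before Day 113 on PC treatment. The last column adds the condition that the grade must exceed the last grade before the first OLE dose.

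| Course (record start day, grade) | OLE TEAE records, start-time rule | With worsening condition |
|---|---|---|
| Day 90 G3, Day 120 G2, Day 140 G1 | 2 | 0 |
| Day 100 G2, Day 125 G1 | 1 | 0 |
| Day 105 G4, Day 118 G3 | 1 (Grade 3) | 0 |
| Day 100 G2, unchanged | 0 | 0 |
| Day 100 G1, Day 120 G2 | 1 | 1 |

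The condition removes the improving records and keeps the true worsening.

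**Step 2: does the general definition already exclude these records?** Its reference point is the first dose of study drug, not the first dose of the period. An event that first appeared in the PC period already satisfies it, so start time alone decides the period. It plainly conflicts with the period rule only for an event that predates the first PC dose and then improves.

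**Step 3: which treatment receives the record?**

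- OLE, switchers from placebo, 15 mg or 45 mg: 75 mg receives an event that arose on something else.
- OLE, 75 mg continuers: the dose is right, but one event appears in both the PC and OLE tables.
- LTE: the record falls in the ≤ 45 mg or ≥ 60 mg group.

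**Step 4: which counts move?** Any-TEAE, SOC/PT and treatment-related participant counts can rise. Grade 3 or higher counts rise only for a step such as Grade 4 to 3. Serious counts rise only if the later record keeps the serious flag.

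**Step 5: scale.** One participant counted only for this reason adds 100 × 1/n percentage points:

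- n = 50: 2.0
- n = 40 (assumed): 2.5
- n = 30 (assumed): 3.3

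Let *a* be the share with an event ongoing at the switch, and *b* the share of those who step down in grade and have no other OLE TEAE. Neither is in the documents. The expected number added to the any-TEAE count is 50 × *a* × *b*:

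- *a* = 0.05, *b* = 0.10: 50 × 0.05 × 0.10 = 0.25 participants, or 0.5 points.
- *a* = 0.10, *b* = 0.30: 50 × 0.10 × 0.30 = 1.5 participants, or 3 points.
- *a* = 0.20, *b* = 0.50: 50 × 0.20 × 0.50 = 5 participants, or 10 points.

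**The case against.** The best reply is that the period sentence only allocates TEAEs to windows, with the general definition just above it still in force. A lower-grade record of a known event is neither a first report nor a worsening, and a documented step-down could be called unequivocally not treatment-emergent, so the default need not catch it. This reading is possible, but the text does not state it. The general definition is also tied to the wrong dose for the purpose (Step 2). A programmer following the sentence as written would flag the record.

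The second reply is that no text says a severity record starts on the date of the grade change. Elsewhere Protocol 9.3 speaks of events that begin or worsen, and sends updates to the existing form. The eCRF completion guidelines mentioned in Protocol 11.2 would settle this and are not available. That limit stands. Even so, the severity sentence is the specific one, covers any change, and calls the result a separate AE, for which a start date is collected.

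The third reply concerns harm, and much of it stands. The tables are descriptive, and no test or power is affected. OLE columns are labelled by sequence and listings show all AEs, so a carried-over event can be traced. The separate summary of participants on 75 mg up to Week 52 runs from the first PC dose, so the PC-to-OLE boundary does not arise there.

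A reader might also infer that serious and Grade 3 or higher counts are inflated generally, or that the comparison of switchers with continuers is biased. The documents support neither. The first needs the particular conditions in Step 4. For the second, one rule applies to all four OLE groups, and nothing shows that carry-over differs between them.

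**Conclusion.** The concern holds in a limited form. Read literally, the two rules turn an improving carry-over into a TEAE of the new period, and no visible text links the records of one event or compares grades across a period boundary. This rests on the new record starting at the grade change, which is inferred.

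The size cannot be fixed from the documents. The firm statement is 2 percentage points for each affected participant in a group of 50. The range of about 0.5 to 10 points applies to the any-TEAE count and depends wholly on the assumed 5–20% with an ongoing event and 10–50% of those stepping down with no other OLE TEAE. A reader who treated every extra record as an extra participant would overstate it, because the overall AE summary counts participants and someone with another OLE TEAE is already in that count.

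This is worth correcting because the misplaced events count against the wrong treatment or appear twice, and the correction is small.

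**What to change.** Amend SAP 9.2.1 in two places.

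1. Define a period TEAE as an AE first reported after that period's first dose, or one whose CTCAE grade rises above its last grade before that dose. For the PC period, the reference is the last grade before the first PC dose.
2. State that consecutive severity records of the same event are joined before flagging, using an eCRF link if one exists, or otherwise the same preferred term with contiguous dates. A record opened only because of a lower grade is then not treatment-emergent in that period, and the default to count does not apply to it.

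The eCRF guidelines should also be checked to confirm which start date a severity record carries.

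The cost is a short SAP change, a small programming step, and some judgement in matching. The documents show no identifier that joins severity records, so matching on term and dates may be needed and will sometimes join or separate records wrongly. No change to data collection is required.

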#### 9.2.2. Adverse Event Summaries

AE will be summarized by treatment groups for the safety population in the PC period, the open-label evaluable population in the OLE period, participants who take INCB054707 75 mg throughout study participation up to Week 52, and the long-term evaluable population in the LTE period.

An overall summary of AEs will include the following:

- Number (%) of participants reporting any TEAEs
- Number (%) of participants reporting any serious TEAEs
- Number (%) of participants reporting any Grade 3 or higher TEAEs
- Number (%) of participants reporting any treatment-related TEAEs
- Number (%) of participants who temporarily interrupted study treatment because of TEAEs
- Number (%) of participants who permanently discontinued study treatment because of TEAEs
- Number (%) of participants who had a fatal TEAE

The following summaries will be produced by MedDRA term (if 10 or fewer subjects appear in a table, a listing may be appropriate):

- Summary of TEAEs by MedDRA SOC and PT
- Summary of TEAEs by MedDRA PT in decreasing order of frequency
- Summary of TEAEs by MedDRA SOC, PT, and maximum severity
- Summary of TEAEs by MedDRA SOC, PT, and CTCAE grade category
- Summary of Grade 3 or higher TEAEs by MedDRA SOC and PT
- Summary of Grade 3 or higher TEAEs by MedDRA PT in decreasing order of frequency
- Summary of serious TEAEs by MedDRA SOC and PT
- Summary of serious TEAEs by MedDRA PT in decreasing order of frequency
- Summary of treatment-related TEAEs by MedDRA SOC and PT
- Summary of treatment-related TEAEs by MedDRA PT in decreasing order of frequency
- Summary of Grade 3 or higher treatment-related TEAEs by MedDRA SOC and PT

- Summary of treatment-related serious TEAEs by MedDRA SOC and PT
- Summary of TEAEs with a fatal outcome by MedDRA SOC and PT
- Summary of TEAEs leading to dose reduction by MedDRA SOC and PT
- Summary of TEAEs leading to dose interruption by MedDRA SOC and PT
- Summary of TEAEs leading to discontinuation of study drug by MedDRA SOC and PT
- Summary of TEAEs requiring concomitant medications by MedDRA SOC and PT

### 9.3. Clinical Laboratory Tests

#### 9.3.1. Laboratory Value Definitions

Laboratory values, change from baseline values, and percent change from baseline values will be summarized descriptively by visit, and non-numeric test values will be tabulated when necessary. Baseline will be determined according to Section 4.1.3. The last record before administration in the highest priority will be considered the baseline record. For baseline laboratory candidates with the same date and time in the same priority category, additional rules may be provided after consultation with the medical monitor to delineate which value will be defined as baseline.

#### 9.3.2. Laboratory Value Summaries

All test results and associated normal ranges from central laboratories will be reported in SI units. All tests with numeric values will have a unique unit per test. Any laboratory test results and associated normal ranges from local laboratories will be converted to SI units.

When there are multiple laboratory nonmissing values for a participant's particular test within a visit window, the laboratory value with the smallest laboratory sequence number will be used in by-visit summaries.

For test results that will be summarized with available normal ranges, the number and percentage of participants with laboratory values being low (but never high), normal, high (but never low), and both low and high will be calculated for each test. This shift summary will be produced for each test. The denominator for the percentage calculation will use the number of participants in the baseline category (ie, low, high, normal, missing) as the denominator for the percentage in each of the categories during the study.

Severity grades will be assigned to laboratory test values based on the numerical component of CTCAE v5. Shift tables will also be presented showing change in CTCAE grade from baseline to the worst grade postbaseline. Separate summaries for abnormally high and abnormally low laboratory values will be provided when the laboratory parameter has both high and low grading criteria. The denominator for the percentage calculation will be the number of participants in the baseline category. The number of participants who experienced worsening of laboratory abnormalities will be summarized by maximum severity.

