Study visits will occur at screening, baseline (Day 1/Week 0), Weeks 2, 4, 6, 8, 12, 16 (EOT1), 18, 20, 22, 24, 28, 32, 36, 40, 44, 48, 52 (EOT2), 56 (EOS, for participants not continuing into the LTE) and early termination if the participant discontinues before Week 16 (ET1) or during the OLE period and before Week 52 (ET2). After Week 52, the study visits during the optional LTE period will occur at Weeks 60, 68, 76, 84, 92, 100 (EOT3), 104 (EOS), and early termination if the participant discontinues during the LTE period and before Week 100 (ET3). Each visit denoted by Week 2, Week 4, Week 6, etc represents a target visit date corresponding to the end of the specified week; therefore, Weeks 2, 4, and 6 respectively represent Days 14, 28, and 42 of the study. Additionally, all participants will be contacted by phone 1 week before the baseline visit (Day 1/Week 0) to ensure that daily assessments are being recorded.

Visits in the LTE are named to reflect continuation from the OLE study, with the first visit of the LTE occurring at Week 52. The eligibility assessment for the LTE occurs at Week 52. Participants who enter the safety-follow period immediately after the Week 52 visit are not allowed to start the LTE period. Participants who are currently tolerating INCB054707 in the OLE, as assessed by the investigator, and who demonstrate willingness and ability to comply with the scheduled visits, will be considered eligible for the LTE period. Furthermore, details on the LTE dose assignment and dose change are described in Section 2.1.5 and Section 6.5.1.

Efficacy will be assessed throughout the study at selected visits (see Table 3). Safety and tolerability will be evaluated throughout the study. Adherence to the study design requirements, including those specified in the SoA (see Table 3), is essential and required for study conduct.

Table 3:Schedule of Activities

		Screening		(1	Placeb	Tre: 00-Col	atmen ntrolle	it ed Per	iod)	T (Open-I	`reatment Label Extensi	on)	Treatn (Long-7 Extens	nent Ferm ion)	Follow-Up
Visit Day/Range	Section	Days -30 to -1	Baseline (W0/Day 1)	W2 ± 3d	W4 ± 3d	W6 ± 3d	W8 ± 3d	W12 ± 3d	W16 ± 3d; EOT1 (or ET1)	W18, W20, W22 and W24; ± 3d	W28-W48, visits every 4 weeks; ± 3d	W52 ± 3d; EOT2 (or ET2)	W60-W92, visits every 8 weeks; ± 7d	W100 ± 7d; EOT3 (or ET3)	W56 + 7d or W104 + 7d; or 28 (+ 7) days after last dose of study drug (EOS)
Administrative Procedure	es														
Informed consent	8.1.1	Х													

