8.3.7. Laboratory Assessments

See Table 10 for the list of clinical laboratory analytes to be performed and Table 3 for the laboratory assessment visit schedule. A central laboratory will perform all clinical laboratory assessments for safety (ie, blood chemistries, hematology assessments, urinalysis, inflammation markers, and lipid panel).

Additional testing may be required by the sponsor based on emerging safety data. All Protocol-required laboratory assessments must be conducted in accordance with the Laboratory Manual and Table 3. Information regarding collection, processing, and shipping of samples for laboratory assessment is provided in the Laboratory Manual.

Clinically significant abnormal laboratory findings are those that are not associated with the underlying disease, unless judged by the investigator to be more severe than expected for the participant's condition. All laboratory tests with values considered clinically significantly abnormal during participation in the study or within 4 weeks after the last dose of study drug should be repeated until the values return to normal or baseline or are no longer considered clinically significant by the investigator or medical monitor.

If screening laboratory assessments are performed more than 30 days before Day 1, then the tests must be repeated and eligibility confirmed before study drug administration on Day 1. Laboratory sample collection on Day 1 must be performed before study drug administration.

See Section 9.1 for information regarding laboratory abnormalities that should be recorded as an AE in the eCRF.

Table 10: Required Laboratory Analytes	Table 10:	Required Laboratory Analytes
--	-----------	-------------------------------------

Chemistry	Hematology	Urinalysis	Serology/Infection	Pregnancy testing

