8.6. Unscheduled Visits

Unscheduled visits may occur at any time at the investigator's (or designee's) discretion, and appropriate clinical and laboratory tests may be performed, as clinically indicated.

If there is a potential clinically significant abnormality in hematology or chemistry assessments (particularly in platelet count) during the study, an unscheduled visit within the following week should occur to repeat laboratory assessments (further details are provided in Table 7 and Section 8.3.7). See Section 6.5.1 for instructions on dose interruption and restart. The investigator must inform and consult the sponsor (or designee) with any hematological abnormality.

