#### 4.1.3. Baseline Value

Baseline is the last nonmissing measurement obtained before the first administration of INCB054707 or placebo in the PC period, unless otherwise defined.

For randomized participants not treated with any study drug, baseline is defined as the last nonmissing assessment before or on the day of randomization for all parameters.

For participants who continue in the OLE period, baseline is defined as follows:

- For efficacy evaluation, baseline is the last nonmissing measurement obtained before the first administration of study drug in the PC period, unless otherwise defined.
- For safety evaluation in the OLE period:
  - For participants who cross over from the placebo group or the INCB054707 15 or 45 mg groups to INCB054707 75 mg, baseline is the last nonmissing measurement obtained before the first administration of INCB054707 75 mg in the OLE period.
  - For participants who take INCB054707 75 mg throughout study participation up to Week 52, baseline is the last nonmissing measurement obtained before the first administration of study drug in the PC period.

For participants who continue in the LTE period, baseline is defined as follows:

- For efficacy evaluation, baseline is the last nonmissing measurement obtained before the first administration of study drug in the PC period, unless otherwise defined.
- For safety evaluation in the LTE period, baseline is the last nonmissing measurement obtained before the first administration of INCB054707 in the LTE period.

When scheduled assessments and unscheduled assessments occur on the same day and the time of the assessment or time of first dose is not available, use the following convention to determine baseline:

- If both a scheduled and an unscheduled visit are available on the day of the first dose and the time is missing, use the scheduled assessment as baseline.
- If all scheduled assessments are missing on the day of the first dose and an unscheduled assessment is available, use the unscheduled assessment as baseline.

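### The by-visit laboratory rule gives the scheduled sample no precedence, so a retest falling early in the next visit's window can replace that visit's scheduled value

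*SAP*

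**What the plan says.** SAP 9.3.2 covers the case "When there are multiple laboratory nonmissing values for a participant's particular test within a visit window" and resolves it thus: "the laboratory value with the smallest laboratory sequence number will be used in by-visit summaries". The supplied text defines neither the visit window nor the sequence number. It does not rank scheduled against unscheduled samples. It provides for local results ("Any laboratory test results and associated normal ranges from local laboratories will be converted to SI units") but does not rank them against central ones, although Protocol 8.3.7 assigns all safety laboratory testing to a central laboratory.

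For baseline the SAP does rank records. Section 4.1.3 deals with a scheduled and an unscheduled record that fall on the first-dose day with the time missing, and says to "use the scheduled assessment as baseline". Section 9.3.1 adds: "The last record before administration in the highest priority will be considered the baseline record". Neither step is carried over to postbaseline visits.

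The extra samples come from the protocol. For a potentially significant hematology or chemistry abnormality, platelets in particular, section 8.6 says that "an unscheduled visit within the following week should occur to repeat laboratory assessments". Section 8.3.7 says that clinically significant abnormal tests "should be repeated until the values return to normal or baseline or are no longer considered clinically significant", without giving an interval between repeats.

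**The concern.** A sequence number identifies a record. It does not show whether the sample was the planned one or how near it lies to the target day. Windows with more than one value will arise mainly in participants with abnormal results, because abnormality is what triggers retesting. Where a retest takes the place of a scheduled sample, an affected participant is summarized at an earlier, event-driven time while the others are summarized near the planned day.

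Timing matters for platelets. Protocol 2.2.1 reports dose-related decreases at 60 mg QD and above in healthy participants, and thrombocytopenia in 4 of 8 HS participants at 90 mg after 4 weeks, and describes the decreases as transient. Hematology is drawn every 2 weeks from Week 2 to Week 8. The same spacing returns at Weeks 16-24, when the placebo, 15 mg and 45 mg participants start 75 mg. At stake is how accurately the by-visit tables describe the time course in each arm, in a study meant to inform the Phase 3 dose.

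**Working it through.** The documents give no figure on this point, so the check is an enumeration of possible timings.

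**Inputs from the documents**
- Target days: the protocol summary (section 1) states that "Weeks 2, 4, and 6 respectively represent Days 14, 28, and 42 of the study". Later visits follow at 7 days per week.
- Visit tolerance: ±3 days in the placebo-controlled and open-label periods (Protocol Table 3).
- First retest: 1 to 7 days after the abnormal sample (Protocol 8.6).

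**Assumptions**
- Sequence numbers rise with collection date.
- A second retest comes 1 to 7 days after the first. The protocol sets no interval.
- Windows are either (A) contiguous with boundaries midway between target days, or (B) the target day ±3.
- All timings are weighted equally. The results are shares of timings and do not predict frequencies.

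**Notation.** The visit with the abnormal result has target day a and the next visit has target day b. The abnormal sample falls on a+k (k = -3 to 3), the first retest on a+k+r (r = 1 to 7), the second on a+k+r+s (s = 1 to 7), and the next scheduled sample on b+k2 (k2 = -3 to 3). Displacement occurs when a retest lies inside the next window and before b+k2.

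**Own retest.** Since r is at least 1, the retest always follows the sample that triggered it and has the larger number. The scheduled sample is kept in 49 of 49 timings, so displacement is 0 of 49.

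**First retest, visits 2 weeks apart (b = a+14)**
- (A) The next window opens on a+8, so k+r must be at least 8. That happens for k=1 with r=7, k=2 with r=6 or 7, and k=3 with r=5, 6 or 7, which is 6 of 49 timings. The latest retest (a+10) precedes the earliest next scheduled sample (a+11), so all 6 displace it: 6/49 = 12%.
- (B) The next window opens on a+11 and the latest retest is a+10, so the share is 0%. For Week 2 the latest retest is Day 14+3+7 = 24, and the Week 4 window opens on Day 25.

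**Second retest, visits 2 weeks apart.** There are 7×7×7×7 = 2401 combinations of k, r, s and k2.
- (A) k+r+s = 8, 9 or 10 arises in 37+36+33 = 106 ways and precedes all 7 next-sample days: 742. For k+r+s = 11 to 16 the ways are 28, 21, 15, 10, 6 and 3, preceding 6, 5, 4, 3, 2 and 1 next-sample days: 168+105+60+30+12+3 = 378. The total is 1120/2401 = 47%.
- (B) Only the 378 remain: 378/2401 = 16%.

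**Visits 4 weeks apart (b = a+28)**
- (A) The next window opens on a+15. A first retest cannot reach it (0%). A second does so for k+r+s = 15, 16 or 17, in 6+3+1 = 10 ways × 7 = 70, and 70/2401 = 3%.
- (B) The next window opens on a+25 and the latest second retest is a+17, so both shares are 0%.

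| Spacing | Windows | First retest | Second retest |
|---|---|---|---|
| 2 weeks | midpoint (assumed) | 12% | 47% |
| 2 weeks | ±3 days | 0% | 16% |
| 4 weeks | midpoint (assumed) | 0% | 3% |
| 4 weeks | ±3 days | 0% | 0% |

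**Example under (A).** A Week 2 sample on Day 16 is abnormal and is retested on Day 22. The Week 4 window opens on Day 22. With the scheduled Week 4 sample on Day 28, the table reports the Day 22 value as Week 4.

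**Non-chronological numbering.** If numbers follow another order, such as data loading, nothing in the rule determines which sample is chosen. Even the sample that prompted the retest could then be replaced.

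**The case against.** The strongest reply is that the rule is prespecified, does not depend on the result, and in the ordinary case does what one would want: with chronological numbers, the scheduled sample beats its own retest. This stands, and it limits the point to the next visit's sample. Hematology and chemistry are also drawn at every scheduled visit, so the next visit may itself serve as the repeat. Parts of the SAP are blacked out, and a window or priority table may exist that cannot be seen. A window table alone would not settle the matter, however, because the rule chooses among values already inside the window.

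Several stronger readings are tempting but unsupported:
- *Every later window holds a retest.* With retest and scheduled days independent and uniform over 7 days, the retest would come first in 21/49 = 43% of cases. The protocol does not prescribe unbroken weekly retesting.
- *A shift in the arm mean can be stated.* One displaced participant among about 50 moves the mean by one fiftieth of the difference between the two values. The documents give neither that difference nor the number of participants affected.
- *SAP 4.1.3 does the opposite.* It only breaks ties between same-day baseline records with a missing time, and says nothing of samples on different days.
- *Local values will often displace central ones.* The local-laboratory sentence concerns unit conversion, and testing is central by protocol.
- *The rule hides a safety signal.* The shift to worst postbaseline CTCAE grade, the maximum-severity summary and the low/high-ever categories do not use the by-visit selection, and potential DILI events are listed. SAP 9.3.3 also counts liver criteria by visit, but the visible text does not say that the 9.3.2 rule governs those counts.

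**Conclusion.** The point holds in a limited form and is minor. SAP 9.3.2 gives the scheduled sample no precedence, and the protocol generates extra samples selectively in participants with abnormal results. With chronological numbering only the next visit's scheduled sample is at risk, mainly at 2-week spacing or after serial retests. The shares above rest on equal weighting of timings, on an assumed interval for second retests and, for the higher figures, on assumed midpoint windows. Without chronological numbering, the selection is arbitrary. Only descriptive by-visit values and changes are affected. Protocol 10.4.3 plans no formal laboratory comparisons between groups.

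**What to change.** In SAP 9.3.2, replace the selection sentence with an ordered rule for by-visit summaries:
1. Use the scheduled-visit value, from the central laboratory if available.
2. If there is none, use the nonmissing value closest to the target day.
3. Use the smallest sequence number only as the final tie-breaker.

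State that unscheduled values remain in the worst-value summaries and listings. If the unredacted SAP does not already define the visit window and the sequence number, the same edit should refer to their definitions. The cost is one SAP sentence and a change to the record-selection code, with no new data.
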